9.5.3 Appropriateness of Measurements

All clinical assessments are standard measurements commonly used in studies of AD.

Standard safety assessments incorporated into this protocol include vital signs, clinical laboratory assessments, physical examinations, ECG measurements, and reports of AEs. MRI will be used to detect vasogenic edema, macrohemorrhage, an area of superficial siderosis, or a symptomatic microhemorrhage and is a standard evaluation to ensure subject safety. The C-SSRS has been endorsed by the FDA as a measure of potential suicidality ([Guidance for Industry Suicidality](#)).

A number of safety aspects have been built into the design of this study in light of the preclinical and clinical safety data with E2609, in addition to mitigating clinical risk in the progression from 14 days of dosing in the MAD study to 18 months of treatment in this Phase 2 study. Details are provided in [Section 9.2.6](#).

9.5.4 Reporting of Serious Adverse Events, Pregnancy, and Events Associated with Special Situations

9.5.4.1 Reporting of Serious Adverse Events

All SAEs, regardless of their relationship to study treatment, must be reported on a completed SAE form by email or fax as soon as possible but no later than 24 hours from when the investigator becomes aware of the event.

SAEs, regardless of causality assessment, must be collected up to 3 months after the last dose of study drug, ie, through to the second follow-up visit (Visit 20). In subjects who discontinue study drug early, but continue with efficacy assessments, SAEs only need to be solicited up to 3 months after the last dose of study drug. However, any SAEs volunteered by subjects after this time point must be reported according to standard procedures. All SAEs must be followed to resolution or, if resolution is unlikely, to stabilization. Any SAE judged by the investigator to be related to the study treatment or any protocol-required procedure should be reported to the sponsor regardless of the length of time that has passed since study completion.

The detailed contact information for reporting of SAEs is provided in the Investigator Study File.

For urgent safety issues, please ensure all appropriate medical care is administered to the subject and contact the appropriate study team member listed in the Investigator Study File.

It is very important that the SAE report form be filled out as completely as possible at the time of the initial report. This includes the investigator's assessment of causality.

Any follow-up information received on SAEs should be forwarded within 1 business day of its receipt. If the follow-up information changes the investigator's assessment of causality, this should also be noted on the follow-up SAE form.

Preliminary SAE reports should be followed as soon as possible by detailed descriptions including copies of hospital case reports, autopsy reports, and other documents requested by the sponsor.

The investigator must notify his/her IRB/IEC of the occurrence of the SAE in writing, if required by their institution. A copy of this communication must be forwarded to the sponsor, or its designee, to be filed in the sponsor's Trial Master File.

9.5.4.2 Reporting of Pregnancy and Exposure to Study Drug Through Breastfeeding

Any pregnancy in which the estimated date of conception is either before the last visit or within 28 days of last study treatment, or any exposure to study drug through breastfeeding during study treatment or within 28 days of last study treatment, must be reported.

If an adverse outcome of a pregnancy is suspected to be related to study drug exposure, this should be reported regardless of the length of time that has passed since the exposure to study treatment.

A congenital anomaly, death during perinatal period, an induced abortion, or a spontaneous abortion are considered to be an SAE and should be reported in the same time frame and in the same format as all other SAEs (see Reporting of Serious Adverse Events [[Section 9.5.4.1](#)]).

Pregnancies or exposure to study drug through breastfeeding must be reported by fax or email as soon as possible but no later than 1 business day from the date the investigator becomes aware of the pregnancy. The contact information for the reporting of pregnancies and exposure to study drug through breastfeeding is provided in the Investigator Study File. The Pregnancy Report Form must be used for reporting. All pregnancies must be followed to outcome. The outcome of the pregnancy must be reported as soon as possible but no later than 1 business day from the date the investigator becomes aware of the outcome.

A subject who becomes pregnant must discontinue study treatment.

9.5.4.3 Reporting of Events Associated with Special Situations

9.5.4.3.1 REPORTING OF ADVERSE EVENTS ASSOCIATED WITH STUDY DRUG OVERDOSE, MISUSE, ABUSE, OR MEDICATION ERROR

Adverse events associated with study drug overdose, misuse, abuse, and medication error refer to AEs associated with uses of the study drug outside of that specified by the protocol. Overdose, misuse, abuse, and medication error are defined as follows:

| | |
|------------------|--|
| Overdose | Accidental or intentional use of the study drug in an amount higher than the protocol-defined dose |
| Misuse | Intentional and inappropriate use of study drug not in accordance with the protocol |
| Abuse | Sporadic or persistent intentional excessive use of study drug accompanied by harmful physical or psychological effects |
| Medication error | Any unintentional event that causes or leads to inappropriate study drug use or subject harm while the study drug is in the control of site personnel or the subject |

All AEs associated with overdose, misuse, abuse, or medication error should be captured on the Adverse Event eCRF and also reported using the procedures detailed in Reporting of Serious Adverse Events ([Section 9.5.4.1](#)) even if the AEs do not meet serious criteria. Abuse is always to be captured as an AE. If the AE associated with an overdose, misuse, abuse, or medication error does not meet serious criteria, it must still be reported using the SAE form and in an expedited manner but should be noted as nonserious on the SAE form and the Adverse Event eCRF.

9.5.4.3.2 REPORTING OF STUDY-SPECIFIC EVENTS

Study-specific events (as detailed in [Section 9.5.1.5.2](#)) should always be considered serious important medical events and be entered on the Adverse Event eCRF and reported using the procedures detailed in Reporting of Serious Adverse Events ([Section 9.5.4.1](#)), even if the study-specific event does not meet other serious criteria.

9.5.4.4 Expedited Reporting

The sponsor must inform investigators (or as regionally required, the head of the medical institution) and regulatory authorities of reportable events, in compliance with applicable regulatory requirements, on an expedited basis (ie, within specific time frames). For this reason, it is imperative that sites provide complete SAE information in the manner described above.

9.5.4.5 Breaking the Blind

In the case of a medical emergency where the appropriate treatment of the subject requires knowledge of the study treatment given, the investigator may break the randomization code for an individual subject. In all such cases, the AE necessitating the emergency blind break will be handled as an SAE in accordance with the procedures indicated above. Any broken code will be clearly justified and documented. The medical monitor must be notified immediately of the blind break.

9.5.4.6 Regulatory Reporting of Adverse Events

Adverse events will be reported by the sponsor or a third party acting on behalf of the sponsor to regulatory authorities in compliance with local and regional law and established guidance. The format of these reports will be dictated by the local and regional requirements.

All studies that are conducted within any European country will comply with European GCP Directive 2005/28/EC and Clinical Trial Directive 2001/20/EC. All SUSARs will be reported, as required, to the competent authorities of all involved European member states.

9.5.5 Completion/Discontinuation of Subjects

A subject may elect to discontinue study drug or withdraw from the study at any time for any reason. All subjects who discontinue taking study drug prematurely for any reason will undergo an ED Visit within 7 days of their last dose of study drug (see [Section 9.1.2.2](#)). In addition, Follow-Up Visits will be scheduled 4 and 12 weeks after the last dose of study drug (Visit 19 and Visit 20, respectively) (see [Section 9.1.2.3](#)). See [Table 7](#) for full details of the assessments to be performed at these visits. Subjects who discontinue study drug prematurely will also be scheduled to return to the study site for each scheduled visit when clinical efficacy assessments are to be conducted (ie, at Visits 11, 14, 15, 16, 17, and 18, if these visits have not already been performed). At these visits, only clinical efficacy assessments (MMSE, CDR, ADAS-cog14, FAQ, CBB and ISLT) will be conducted. Subjects who discontinue early from study drug are considered on study as long as they return for their regularly scheduled clinical efficacy visits as outlined above. Subjects who discontinue study drug early (as opposed to subjects whose dosing with study drug is temporarily suspended under Medical Monitor guidance) will not be permitted to restart study drug.

The investigator will promptly explain to the subject involved that the study will be discontinued for that subject and will provide appropriate medical treatment and other necessary measures for the subject. A subject who has ceased to return for visits will be followed up by mail, phone, or other means to gather information such as the reason for failure to return, the status of treatment compliance, the presence or absence of AEs, and clinical courses of signs and symptoms.

Subjects who withdraw prematurely from the study will be withdrawn for 1 of these primary reasons: AE(s), lost to follow-up, subject choice, inadequate therapeutic effect, withdrawal of consent, pregnancy, study terminated by sponsor, or other. In addition to the primary reason, the subject may indicate 1 or more secondary reason(s) for withdrawal from the study. Study disposition information will be collected on the Subject Disposition eCRF.

A subject removed from the study for any reason may not be replaced.

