9.4.7 Prior and Concomitant Therapy

Medication (including over-the-counter medications) or therapy administered to the subject before the study (within 6 months of randomization) and during the study (starting at the date of informed consent) will be recorded on the Prior & Concomitant Medication eCRF or Non-Pharmacological Procedures eCRF. The investigator will record on the Adverse Event eCRF any AE for which the concomitant medication/therapy was administered. If the concomitant medication/therapy is being administered for a medical condition present at the time of entry into the study, the investigator will record the medical condition on the Medical History and Current Medical Condition eCRF.

Listings of prohibited and permitted drugs are provided in [Appendix 2](#). Prohibited medications are presented in [Listing 1](#), [Listing 2](#), [Listing 3](#), [Listing 4](#), [Listing 5](#), and [Listing 6](#). Medications that are permitted with restrictions are listed in [Listing 7](#), [Listing 8](#), and [Listing 9](#).

The following agents are not permitted before randomization (specific timeframes are shown below) and throughout the study until after the last treatment visit:

- Anticoagulants (eg, warfarin, digabatin) are not permitted for a period of 5 half-lives or 7 days (whichever is longer) before randomization
- Drugs which may cause QTc prolongation are not permitted for a period of 5 half-lives or 14 days (whichever is longer) before randomization
- Strong CYP3A4 inhibitors are not permitted for a period of 5 half-lives or 14 days (whichever is longer) before randomization
- Live vaccines are not permitted within 3 months before randomization. This does not apply to non-live/inactivated vaccines
- Ig therapy and biologic drugs are not permitted within 6 months before randomization

- Systemic or ocular immunosuppressive or immunomodulatory drugs are not permitted for a period of 5 half-lives or 60 days (whichever is longer) before randomization

Subjects taking AChEIs or memantine must meet the following criteria in order to be included in the primary analyses:

- On a stable dose for 12 weeks before the Baseline cognitive assessments at Visit 2
- Remain on a stable dose while on study

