| Nominal months elapsed since first dose | 0 | | | | 1 | | 2 | | 3 | 4 | 5 | 6 | 9 | 12 | 15 | 18 | | 19 | 21 | | |
| Procedures/ Assessments | | | | | | | | | | | | | | | | | | | | | |
| Routine physical examination | X | | | | X | | X | | X | | | X | X | X | X | X | X | X | X ^e | X | |
| Inclusion and Exclusion criteria | X | | | | | | | | | | | | | | | | | | | | |
| Vital signs ^f | X | X | X | X | X | X | X | X | X | X | X | X | X | X | X | X | X | X | X ^e | X | |
| Respiratory rate | | | | | X | | X | | X | X | X | X | X | X | X | X | X | X | X ^e | X | |
| Weight | | | | | | | | | X | | | X | X | X | X | X | X | | X | X | |
| Centralized dermatological assessment via photography ^g | | | | | | | | | X | | | X | X | X | X | X | X | | X | X | |
| Neurological examination ^h | | | | | | | | | | | | X | | X | | X | X | X | X | X | |
| Ophthalmic examination ⁱ | | | | | | | | | | | | | | | | | | | | X | |
| Concomitant medications ^j | | X | X | X | X | X | X | X | X | X | X | X | X | X | X | X | X | X | X | X | |
| 12-lead ECG ^k | | | X | | X | | X | | X | | | X | | X | | X | X | X | X ^e | X | |
| Clinical biochemistry and urinalysis | | | X | | X | | X | | X | | | X | X | X | X | X | X | X | X ^e | X | |
| Complete blood count | | X | X | X | X | X | X | X | X | X | X | X | X | X | X | X | X | X | X ^e | X | |
| Blood samples for lymphocyte subset analyses ^l | | X | X | X | X | X | X | X | X | X | X | X | X | X | X | X | X | X | X ^e | X | |
| Blood samples for Igs ^m | | | | | X | | X | | X | | | X | | X | | X | X | X | X ^e | X | |
| Blood samples for isolation of PBMCs | | | X | | | | | | X | | | | | | | | | | X | | |
| Urine pregnancy test (females of CBP only) | X ⁿ | | | | | | | | X | | | X | X | X | X | X | X | X | | X | |
| Blood sample for storage for immune status ^o | | | | | X | | | | X | | | X | | X | | X | X | X | X | X | |
| CBB and ISLT ^p | | | | | | | | | X | | | X | X | X | X | X | X | X | X | | |
| MMSE ^p | | | | | | | | | X | | | X | X | X | X | X | X | X | X | | |
| CDR ^p | | | | | | | | | X | | | X | X | X | X | X | X | X | X | | |
| ADAS-cog ₁₄ ^p | | | | | | | | | X | | | X | X | X | X | X | X | X | X | | |

Table 7 Schedule of Procedures/Assessments in Study 202: Randomization Phase (Visit 3 through Visit 20)

| Phase | Randomization | | | | | | | | | | | | | | | | | | | UNS Visit ^d |

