9.7.1.5 Prior and Concomitant Therapy

All investigator terms for medications recorded in the eCRF will be coded to an 11-digit code using the World Health Organization Drug Dictionary (WHO DD) (Mar 2014). The number (percentage) of subjects who took prior and concomitant medications will be summarized on the Safety Analysis Set by treatment group, Anatomical Therapeutic Chemical class, and WHO DD preferred term. Prior medications will be defined as medications that stopped before the first dose of study drug. Concomitant medications will be defined as medications that (1) started before the first dose of study drug and were continuing at the time of the first dose of study drug, or (2) started on or after the date of the first dose of study drug up to the date of the last dose. All medications will be presented in subject data listings.

Medications taken within the 12-week Follow-Up period will also be recorded.

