9.7.1.6.1 PRIMARY EFFICACY ANALYSIS

Primary analysis of primary endpoint

The primary analysis will be based on MCI/Prodromal subjects from the FAS with the prespecified censoring rule applied. The primary endpoint is the change from baseline to 18 months in the derived ADCOMS. The dose-response of the primary endpoint is modelled with a first-order normal dynamic linear model, where Normal and Inverse-Gamma priors are used. The primary efficacy analysis will calculate the Bayesian posterior probability that the dose identified is the most likely ED₉₀ dose that achieves 25% improvement over the placebo arm. At each interim analysis and the final analysis, 2 Bayesian probabilities will be summarized for each active dose: the probability it is the ED₉₀ dose and the probability of achieving 25% improvement over the placebo arm.

For the clinical efficacy data (ie, derived ADCOMS, MMSE, CDR, ADAS-cog, CBB, ISLT, and FAQ) subjects will be censored at the time of initiation of treatment with AChEIs or memantine, if they were not on these medications at the time of Baseline cognitive assessment (Visit 2), and will be censored at the time of dose adjustment of AChEIs or memantine if they were already on stable treatment with these medications at the time of Baseline cognitive assessment (Visit 2). The value of the primary endpoint for censored subjects will be imputed using data up to the censoring time and Bayesian longitudinal modeling.

Sensitivity analysis of primary endpoint

After unblinding, the primary endpoint will be analyzed using the Bayesian methods described above as well as conventional statistical methods. The following additional Bayesian analyses will be conducted as sensitivity analyses:

- The primary endpoint will be analyzed regardless of initiation of treatment, or dose adjustment, with AChEIs or memantine using the same Bayesian analysis method as primary analysis. This is an intent-to-treat analysis without any censoring.
- In case of early success, the primary analysis as well as the above sensitivity analyses will be repeated after all subjects have completed 18 months of treatment or have been lost to follow-up.

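### After Visit 20 no medication review is scheduled for subjects who stopped study drug early, although the primary censoring rule needs AChEI/memantine dates through Month 18

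*Protocol*

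**What the plan says.** **Visits after drug stop.** The Synopsis (Early Discontinuation), 9.1.2.2, 9.3.3, 9.5.5 and Table 7 note b all bring early stoppers back for efficacy visits "at Visits 11, 14, 15, 16, 17, and 18, if these visits have not already been performed". All five limit the content of these visits: "only clinical efficacy assessments (MMSE, CDR, ADAS-cog14, FAQ, CBB and ISLT) will be conducted". Section 9.5.5 also fixes their status: "Subjects who discontinue early from study drug are considered on study as long as they return for their regularly scheduled clinical efficacy visits".

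**Censoring.** Section 9.7.1.6.1 states that "subjects will be censored at the time of initiation of treatment with AChEIs or memantine" if they were not on these drugs at Baseline, and at dose adjustment if they were. The endpoint is then imputed from data before that date. Nothing in the rule stops at the last dose of study drug.

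**Medication recording.** Section 9.4.7 says that medication given "during the study (starting at the date of informed consent) will be recorded on the Prior & Concomitant Medication eCRF", with no end date. In Table 7 the row "Concomitant medications ^j" is marked at Visits 4 to 18, the Early Discontinuation Visit, Visits 19 and 20, and unscheduled visits. Section 9.7.1.5 defines concomitant medications to include those that "started on or after the date of the first dose of study drug up to the date of the last dose" and adds: "Medications taken within the 12-week Follow-Up period will also be recorded".

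**The concern.** A censoring rule works only if the event that triggers it is dated over the whole period in which outcome values are used. For subjects still on drug, Table 7 schedules a medication review at every efficacy visit. For early stoppers, the scheduled reviews end 12 weeks after last dose, while ADCOMS collection continues to Month 18.

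If an AChEI or memantine is started or its dose changed in that interval and nobody asks, the later ADCOMS values enter the primary Bayesian model uncensored, contrary to the stated rule. The same event in a subject still on drug would be dated and censored. The statistical analysis plan cannot repair this later, because it cannot supply dates that were never collected.

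**Working it through.** The protocol gives no figure to reproduce. The check is a visit count followed by a comparison of the text.

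**Inputs.** Table 7 days: Visit 11 = 85, Visit 14 = 183, Visit 15 = 274, Visit 16 = 365, Visit 17 = 456, Visit 18 = 547. For an early stopper, Visit 19 is at last dose + 28 days and Visit 20 at last dose + 84 days (9.5.5: 4 and 12 weeks). An efficacy visit within 8 days of Visit 19 or 20 need not be attended (9.1.2.2).

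**Which visits fall after the last scheduled review?** An efficacy visit on day d lies more than 8 days after Visit 20 when d − (L + 84) ≥ 9, where L is the day of last dose. That is, L ≤ d − 93.

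| Visit | d − 93 | Efficacy visits after Visit 20 if L is no later than this |
|---|---|---|
| 14 | 183 − 93 = 90 | 5 (Visits 14–18) |
| 15 | 274 − 93 = 181 | 4 |
| 16 | 365 − 93 = 272 | 3 |
| 17 | 456 − 93 = 363 | 2 |
| 18 | 547 − 93 = 454 | 1 |

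For Visit 11, 85 − 93 = −8, so it can never fall in the gap. With a last dose after day 454 the gap contains no efficacy visit.

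**Example with five visits in the gap.** Last dose on day 85 puts Visit 20 on day 85 + 84 = 169. Visits 14 to 18 all follow. The interval from Visit 20 to Visit 18 is 547 − 169 = 378 days, or 54 weeks.

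**Total visits after drug stop.** This can be six, because Visit 11 may still be due. With last dose on day 20, Visit 11 (day 85) comes before Visit 20 (day 104), so a scheduled review still follows it. Five is the maximum for visits after Visit 20, not for all visits after drug stop.

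**The text after Visit 20, side by side.**
- Pointing to no collection: the word *only* in five places, and the 12-week reach of the recording sentence in 9.7.1.5. In Appendix 2, Listing 7 also runs its stable-dose condition for cognitive enhancers to the second Follow-Up Visit, which for an early stopper is the same point.
- Pointing to collection: 9.4.7, read with the on-study status in 9.5.5.
- Needing collection: 9.7.1.6.1, for every ADCOMS value through Month 18.

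The first group is visit-specific and is what a site would work from. The second is a general duty with no scheduled inquiry attached.

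**The case against.** The strongest reply is that recording is already required. Section 9.4.7 covers the whole study, and 9.5.5 says these subjects are on study while they keep returning. Where the protocol wants a cut-off for off-drug subjects it states one, as it does for adverse events in 9.5.1.5.1 (3 months after last dose). It states none for medication in 9.4.7. Section 9.7.1.5 defines categories for summary tables, and its follow-up sentence can be read as adding to recording, not ending it. Section 9.5.7 has the investigator ask at each visit about care from another physician. The Bayesian sensitivity analysis without censoring needs no medication dates at all.

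Much of this stands. A reader might infer that every start after drug stop goes unrecorded and that the rule cannot be applied to these subjects. The documents do not support that. Starts in the first 12 weeks are picked up at the Early Discontinuation Visit, Visit 19 and Visit 20, and 9.4.7 gives a basis for recording later ones.

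It does not close the gap. A general duty to record does not schedule the question, and five passages tell the site to do the scales only. Section 9.5.7 serves to inform the other physician; it does not ask for drug, start date or dose change. The uncensored analysis cannot reveal a missed start, since for those values it and the primary analysis use the same data.

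Two limits apply. The quoted text is that of Version 3.0 (Amendment 01). Appendix pages marked with Amendment 02 are also in the file, but not that version's main text, so a later change of wording cannot be checked. The eCRF and its completion guidelines are not shown either.

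**Conclusion.** The point holds as a conflict between passages with a consequence for the primary analysis. After Visit 20, scheduled medication review ends for early stoppers, while the censoring rule still depends on AChEI/memantine start and dose-change dates. One to five ADCOMS visits fall in that gap when the last dose is by about day 454, and five when it is by about day 90. The count rests on nominal Table 7 days and the 8-day skip rule; visit windows would shift the cut-offs by some days.

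No effect size can be given. A reader might multiply the 20% attrition figure in 9.7.2.1 by some share of stoppers who start these drugs. That figure is an assumption for vMRI power, not a rate of stopping drug while staying on study, and the documents give no rate of later AChEI/memantine starts. A reader might also infer that the gap favours the higher doses, because several stopping criteria track possible drug effects. No figure in the protocol shows stopping or later starts concentrating by dose, and inadequate therapeutic effect is also a listed reason for leaving. The direction is unknown.

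This is a cheap improvement: worth making because uncollected dates cannot be recovered, but not evidence that the primary analysis fails.

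**What to change.** In the Synopsis, 9.1.2.2, 9.3.3, 9.5.5 and Table 7 note b, add recording of AChEI and memantine use, with start, stop and dose-change dates, to what is done at efficacy visits after drug stop. In 9.7.1.5, extend recording of these drugs to the last efficacy visit attended, so that it agrees with 9.4.7 and covers every ADCOMS value to which 9.7.1.6.1 applies.

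The cost is one dated question at visits already attended, plus eCRF and amendment wording. No visit or procedure is added, and treatment does not change.
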